### ***Medical or surgical history***

Medical or surgical history includes all the relevant medical or surgical history during the lifetime of the patient.

The information will be coded using the version of Medical Dictionary for Regulatory Activities (MedDRA) currently in effect at Sanofi at the time of database lock.

The medical and surgical history will be summarized by treatment group and overall, and by system organ class (SOC) and preferred term (PT) sorted by internationally agreed order of SOC and by the decreasing frequency of PT within SOC based on the overall incidence across treatment groups.

Comorbidity history will be summarized separately. The following comorbid diseases will be summarized:

- Atopic dermatitis history (Yes, Ongoing condition).
- Allergic conjunctivitis history (Yes, Ongoing condition).
- Allergic rhinitis history (Yes, Ongoing condition).
- Allergic conjunctivitis and/or rhinitis history (Yes, Ongoing condition).
- Chronic rhinosinusitis history (Yes, Ongoing condition).
- Nasal polyps history (Yes, Ongoing condition).
- Eosinophilic esophagitis history (Yes, Ongoing condition).
- Food allergy history (Yes, Ongoing condition).
- Hives history (Yes, Ongoing condition).

In addition, a patient will be considered to have ongoing atopic medical condition if he/she has any of the following ongoing conditions: atopic dermatitis, allergic conjunctivitis, allergic rhinitis, eosinophilic esophagitis, food allergy, hives; or has baseline total IgE  $\geq 100$  IU/mL and at least one aeroantigen specific IgE is positive ( $\geq 0.35$  IU/mL) at baseline. Ongoing atopic medical condition will be summarized by treatment group and overall.

### ***Disease characteristics***

The following baseline disease characteristics will be summarized by treatment group and overall:

- ICS dose level (medium, high as defined in [Appendix B](#)).
- Age of asthma onset (quantitative and in classes: <18 years, ≥18-<40, ≥40 years).
- Time since first diagnosis of asthma (years).
- Time since last severe asthma exacerbation (months); a severe asthma exacerbation prior to the study is defined as any treatment with 1 systemic (oral or parenteral) steroid burst or more for worsening asthma or hospitalization or an emergency/urgent medical care visit for worsening asthma.
- Number of severe asthma exacerbation experienced within 1 year before Visit 1 (quantitative variable and qualitative variables: 0, 1, 2, 3, ≥4).
- Number of severe asthma exacerbations requiring hospitalization or urgent medical care experienced within 1 year before Visit 1 (quantitative variable and qualitative variables: 0, 1, 2, 3, ≥4).
- Smoking history (Never, Former), time since cessation of smoking (years) and smoking quantity in pack-years for former smokers.
- Baseline spirometry data including pre-bronchodilator Forced Expiratory Volume in One Second (FEV1, in L, quantitative and in class: ≤1.75 and >1.75L), percent predicted FEV1 (%), quantitative and in class: <60% and ≥60%), post bronchodilator FEV1 (L) and FEV1 reversibility (%).
- AM and PM Peak Expiratory Flow (PEF) (L/min).
- AM and PM symptom scores.
- Asthma control questionnaire 5-question version (ACQ-5) score (quantitative and in classes : ≤2 and >2).
- Number of inhalations/day of salbutamol/albuterol or levosalbutamol/levalbuterol for symptom relief in a 24-hr period.
- Hypersensitivity to aspirin or nonsteroidal anti-inflammatory drug (NSAID; Yes, Ongoing condition).
- Blood eosinophils (quantitative and in class: <0.15 and ≥0.15 Giga/L; <0.3 and ≥0.3 Giga/L).
- FeNO in ppb (quantitative and in class: <50 and ≥50 ppb).
- Total IgE in IU/mL.

### 2.3.2 Baseline pharmacodynamics parameters

The baseline PD biomarker parameter is defined as the last non-missing value prior to the first dose of IMP unless otherwise specified (see [Section 2.6.1](#) for more details).

All baseline PD biomarker parameters are presented along with the post-baseline PD biomarker summary statistics by treatment group separately in the PD populations.

No statistical testing on the baseline PD parameters will be performed.

### **2.3.3 Baseline efficacy parameters**

The baseline value of spirometry parameters and ACQ5 score is defined as the last available value up to Week -2 to -0.5 before the bronchoscopy unless otherwise specified.

The baseline AM PEF is the mean of available AM measurements recorded for the 7 days up to Week -2 to -0.5 before bronchoscopy, and the baseline PM PEF is the mean of available PM measurements recorded for the 7 days up to Week -2 to -0.5 before bronchoscopy.

All baseline efficacy parameters are presented along with the post-baseline efficacy parameters summary statistics by treatment group.

No statistical testing on baseline efficacy parameters will be performed.

### **2.3.4 Baseline safety parameters**

The baseline value of safety parameters is defined as the last available value prior to the first dose of IMP. No specific description of the safety parameters will be provided at baseline. If relevant, the baseline values will be described along with each safety analysis.

## **2.4 EXTENT OF STUDY TREATMENT EXPOSURE AND COMPLIANCE**

The extent of study treatment exposure and compliance will be assessed and summarized by actual received treatment within the safety population.

### **2.4.1 Extent of study treatment exposure**

The extent of IMP exposure will be assessed by the duration of IMP exposure. Duration of IMP exposure in days is defined as: last dose date - first dose date + 14 days, regardless of unplanned intermittent discontinuations (see [Section 2.11.5](#) for calculation in case of missing or incomplete data).

Duration of IMP exposure will be summarized descriptively as a quantitative variable (number, mean, SD, median, minimum, and maximum).

### **2.4.2 Compliance**

A given administration will be considered noncompliant if the patient did not take the planned dose of treatment as required by the protocol. No imputation will be made for patients with missing or incomplete data.

Percentage of compliance for a patient will be defined as the number of administrations that the patient was compliant divided by the total number of administrations the patient was planned to take during the treatment period (i.e., from the first to the last administration).

Treatment compliance will be summarized descriptively as quantitative variables (number, mean, SD, median, minimum, and maximum). If needed, the percentage of patients whose compliance is < 80% will be summarized.

## 2.5 PRIOR/CONCOMITANT MEDICATION/THERAPY

All medications taken within 3 months before screening and until the end of the study, including asthma controller medications and systemic corticosteroids, are to be reported in the case report form (CRF) pages.

All medications will be coded using the World Health Organization-Drug Dictionary (WHO-DD) version currently in effect at Sanofi at the time of database lock.

- Prior medications are those the patient used prior to the first IMP injection. Prior medications can be discontinued before the first administration or can be ongoing during treatment phase.
- Concomitant medications are any treatments received by the patient concomitantly to the IMP, from the first administration of IMP to the last administration of IMP + 98 days or till rollover to the OLE study.
- Post-treatment medications are those the patient took in the period from the last administration of IMP + 99 days to the end of the study.

A given medication can be classified as a prior medication, concomitant medication and post-treatment medication at the same time.

The prior and concomitant medications will be presented for the randomized population.

Medications will be summarized by treatment group according to the WHO-DD dictionary, considering the first digit of the anatomic category (ATC) class (anatomic category) and the first 3 digits of the ATC class (therapeutic category). All ATC codes corresponding to a medication will be summarized, and patients will be counted once in each ATC category (anatomic or therapeutic) linked to the medication. Therefore patients may be counted several times for the same medication.

The table for prior medications will be sorted by decreasing frequency of ATC followed by all other therapeutic classes based on the overall incidence across treatment groups. In case of equal frequency regarding ATCs (anatomic or therapeutic categories), alphabetical order will be used.

Concomitant medication received during the first IMP to the last IMP + 14 days and concomitant medication received during the first IMP to the last IMP + 98 days will be summarized separately. The tables for concomitant medications will be sorted by decreasing frequency of ATC followed

by all other therapeutic classes based on the incidence in the dupilumab group. In case of equal frequency regarding ATCs (anatomic or therapeutic categories), alphabetical order will be used.

In addition, following treatments will be summarized separately:

- ICS in combination with other controllers and reliever medications
- Prednisone/prednisolone prescribed post-bronchoscopy

### 2.5.1 ICS in combination with one or two other controllers

On a daily basis throughout the study, the patient uses an electronic diary to record daily use of ICS in combination or concurrently with other controllers as used just prior to screening.

ICS and other asthma controller medications will be identified as the medications reported on the “Prescribed Asthma Controller Medications” eCRF page.

The total daily dose of ICS in asthma controller medication at randomization will be classified as medium-dose or high-dose according to [Appendix B](#). If a patient takes more than one medication containing ICS, the ICS dose of different products will be standardized according to equivalent dose specified in [Table 2](#). The equivalent dose is determined based on the thresholds in [Appendix B](#). After conversion, the total daily dose for inhaled corticosteroid will be calculated and classified as medium or high dose.

**Table 2 – Equivalent dose for inhaled corticosteroids for adults**

Inhaled corticosteroid	Equivalent dose (mcg) to 500 mcg Fluticasone propionate (DPI or HFA)
FLUTICASONE FUROATE	200-*
BECLOMETASONE DIPROPIONATE (CFC)	1000
BECLOMETASONE DIPROPIONATE (HFA)	400
BUDESONIDE (DPI)	800
CICLESONIDE (HFA)	320
MOMETASONE FUROATE	440
TRIAMCINOLONE ACETONIDE	2000

ADAPTED FROM GINA 2016 GUIDELINES

HFA=hydrofluoroalkane, DPI= Dry Powder Inhaler

\*Fluticasone furoate (FF) dose  $\geq$  200 mcg is converted to equivalent fluticasone propionate (DPI or HFA) dose of  $(FF \text{ dose} + 1) \times 2.5$ ; FF dose  $<$ 200 mcg is converted to equivalent fluticasone propionate (DPI or HFA) dose of  $FF \text{ dose} \times 2.5$ .

Example: A patient received 400 mcg budesonide (DPI) and 440 mcg mometasone furoate. They are equivalent to 250 mcg and 500 mcg fluticasone propionate correspondingly. The combined total daily dose is equivalent to 750 mcg fluticasone propionate and classified as high dose.

Number of controllers taken by each patient will be counted by therapeutic drug class. All drugs in a therapeutic class will be only counted once.

## Description of controller medications

Prior asthma controller medications will be summarized by treatment group sorted by decreasing frequency of standard medication name on the incidence in the overall treatment group.

Concomitant asthma controller medications will be summarized by treatment group sorted by decreasing frequency of standard medication name on the incidence in treatment group.

Number and percentage of patients on high-dose ICS, medium-dose ICS, and any non-ICS controller medication, LABA, long-acting muscarinic antagonist (LAMA), and LTRA at baseline will also be summarized.

## Compliance for controller medications

During the study, the daily intake of each prescribed asthma controller medication will be recorded on the electronic diary every evening. Compliance for the controller medications with ICS component and overall compliance to all prescribed controller medications will be calculated for each patient. For each day, a patient is considered as compliant to the prescribed controller medication with ICS component if the actual dose of each controller medication with ICS component is the same as or greater than the prescribed dose. Similarly, a patient is considered as compliant to all controller medication if the actual dose of each controller medication is the same as or greater than the prescribed dose. Following compliances will be calculated and summarized by treatment group:

- **Compliance for controller medication(s) with ICS component** is defined as the number of days when the patient is compliant to the prescribed controller medication(s) with ICS component divided by the number of days the patient stays in the treatment period (from the first dose to the last dose + 14 days).
- **Overall controller medication(s) compliance** is defined as the number of days when the patient is compliant with all prescribed controller medication divided by the number of days the patient stays in the treatment period.

### 2.5.2 Reliever medication

Patients may administer albuterol/salbutamol or levalbuterol/levosalbutamol metered dose inhaler (MDI) as reliever medication as needed during the study. Nebulizer solutions may be used as an alternative delivery method.

Salbutamol/albuterol nebulizer and levosalbutamol/levalbuterol nebulizer use recorded in the electronic diary will be converted to the number of puffs as shown on the [Table 3](#).

**Table 3 - Conversation table for reliever medication: Salbutamol/Albuterol Nebulizer Solution**

Salbutamol/Albuterol Nebulizer Solution -Total Daily Dose (mg)	Number of puffs*
2.5	4
5.0	8
7.5	12
10	16

\*Conversion factor: salbutamol/albuterol nebulizer solution (2.5 mg) corresponds to 4 puffs

Example of salbutamol/albuterol Nebulizer-to-Puff Conversion: Patient received 3 salbutamol/albuterol nebulizer treatments (2.5 mg/treatment) between 7 and 11 AM. Total daily = 7.5 mg, i.e., 12 puffs.

**Table 4 - Conversation table for reliever medication: Levosalbutamol/Levalbuterol Nebulizer Solution**

Levosalbutamol/Levalbuterol Nebulizer Solution -Total Daily Dose (mg)	Number of puffs*
1.25	4
2.5	8
3.75	12
5	16

\*Conversion factor: levosalbutamol/levalbuterol nebulizer solution (1.25 mg) corresponds to 4 puffs

Example of levosalbutamol/levalbuterol Nebulizer-to-Puff Conversion: Patient received 3 levosalbutamol/levalbuterol nebulizer treatments (1.25 mg/treatment) between 7 and 11 AM. Total daily = 3.75 mg, i.e., 12 puffs.

Descriptive statistics on the number of puffs of reliever medications by 24 hours will be provided by treatment group and visit.

## **2.6 ANALYSIS OF PHARMACODYNAMIC VARIABLES**

Pharmacodynamic analyses will be performed on the bronchoscopy or on the secondary PD population, depending on the biomarkers.

All values will be assigned to the theoretical visit; unscheduled visit measurements will be included in the computation of baseline if occurred before the 1st IMP, but will not be included in any by-visit summaries or statistical models (only scheduled values will be taken into account).

Only data measured before or on the last IMP date + 14 days (on-treatment period) will be taken into account in all analyses.

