### **1.1 STUDY DESIGN AND RANDOMIZATION**

PDY14192 is a Phase 2a, exploratory, multinational, multicenter, randomized, double-blind, placebo-controlled, parallel group study of repeated doses of dupilumab or placebo administered subcutaneously (SC) every 2 weeks (q2w) for 12 weeks in adult patients with persistent asthma who are receiving at minimum a medium to high dose of inhaled corticosteroid (ICS) in combination with long-acting beta-agonists (LABA). Patients requiring a third asthma controller are eligible. Both the patients and investigators will be blinded to assigned active drug or matching placebo.

After a screening phase of up to 6 weeks (5 weeks and optional addition of 7 days), patients will be centrally randomized (using allocation from block randomization schedule) via Interactive Voice Response System/Interactive Web Response System (IVRS/IWRS) in a 1:1 randomization ratio to dupilumab 300 mg q2w in 2 mL or placebo q2w in 2 mL. Randomization will be stratified by ICS dose level (medium, high) and region (North America, Europe).

During the study, patients will undergo 2 bronchoscopy procedures (one prior to the initiation of study drug and the other after 12 weeks of treatment) for the collection of bronchial biopsy, bronchial brushing and bronchoalveolar lavage fluid samples.

Approximately 42 patients will be randomized to dupilumab or placebo (around 21 patients per group) with at least 21 patients receiving treatment with high dose of ICS and no more than 8 patients with baseline blood eosinophils < 150 cells/ $\mu$ L (i.e., 0.15 Giga/L).

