### 1.3 DETERMINATION OF SAMPLE SIZE

The sample size and the statistical power are estimated based on the pharmacodynamics (PD) endpoint of fractional exhaled nitric oxide (FeNO) as a surrogate marker for airway inflammation as no historical data was available on the main endpoints of bronchial inflammatory cells at the time of the protocol writing no historical data is available on the main endpoints of bronchial inflammatory cells.

The following assumptions are used for the estimations:

- A difference of 25 parts per billion (ppb) in the change from baseline in FeNO at Week 12/end of treatment (EOT) between dupilumab and placebo, and a common standard deviation (SD) of 32 ppb (this corresponds to a hypothesized effect size of 0.78)
- A t-test at 1-sided  $\alpha=0.05$
- Not accounting for early dropout, i.e., the calculated sample size refers to the number of completers who have baseline and Week 12/ EOT bronchoscopy measurements and have adequate biopsies (i.e., of sufficient quality, from which quantitative results are available for at least one of the biomarkers tested) for analysis at both baseline and Week 12/EOT.

Based on above assumptions, it is estimated that, with a total of 42 completers with adequate biopsy samples (21 completers per group), the study will have an 80% power to detect a difference of 25 ppb in the change from baseline in FeNO at Week 12/EOT between dupilumab and placebo.

Based on observations in other clinical trials (see Section 9.5 of the study protocol), it is expected that this sample size will be sufficient to evaluate the main PD endpoints in bronchial submucosa. Brightling et al (1) powered their study to show a reduction in airway submucosal eosinophils from baseline to Week 12 for their active drug compared with placebo using the following SD of the log values of the ratio vs. baseline in the change in number of eosinophils per mm^2 of subepithelial tissue in bronchial biopsy: 1.62 for the active group and 1.82 for placebo

Using an estimate of the SD of the log of the ratio in both groups of 1.7, it is calculated that 21 patients per group (planned sample size of the PDY14192 study) would be sufficient to detect a 3.8-fold decrease (corresponding to a hypothesized effect size of 0.78 in log of ratio) compared with placebo with 80% power (one-sided test at 5%).

[figure not shown]
The calculations were made using nQuery Advisor 7.0.

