## 1.4 STUDY PLAN

The clinical trial consists of three periods:

- **Screening Period** (5 weeks and potentially additional up to 7 days): to determine a patient's eligibility status or scheduling of bronchoscopy and establish the level of asthma control before randomization. During the screening period, a bronchoscopy procedure is performed to acquire baseline samples.
- **Randomized Treatment Period** (12 weeks and potentially additional up to 4 weeks in the case the bronchoscopy at week 12 has to be postponed to week 14 or 16): to treat with dupilumab or placebo SC injection.
- **Post-treatment Period** (12 weeks): to monitor patients' statuses when off study drug treatment for patients not participating in the open label extension (OLE) LTS12551 study. Eligible patients participating in the OLE study will enter the study after completion of the EOT visit assessments. The post-treatment analyses for patients who enter the OLE study will be described in a separate SAP.

Figure 1 - Graphical study design

\*R: Randomization 1:1  
BC: Bronchoscopy  
IMP: Investigational Medicinal Product administration  
EOT: End-Of-Treatment visit  
EOS: End-Of-Study visit  
Visit windows for visits after Day 1 are +/- 3 days  
\*\*If a patient is unable to undergo a bronchoscopy at Week 12, the EOT visit may be postponed and up to 2 additional doses of IMP may be administered.

Refer to the [Appendix A](#) for the detailed study flow chart.

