### **2.2.1 Pharmacodynamic populations**

Two PD populations will be defined:

- The bronchoscopy PD population will encompass all randomized and treated patients with an evaluable bronchoscopy performed at baseline and at Week 12/EOT; this population will be used for the analyses of the bronchoscopy PD endpoints;
- The secondary PD population will encompass all randomized and treated patients; this population will be used for the analyses of other PD endpoints.

Patients treated without being randomized will not be included in any PD populations.

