### 2.6.1.1 Main endpoints

The following inflammatory cells measured in biopsy samples by IHC will be considered as the main markers:

- Eosinophils, based on major basic protein (MBP) positive cells; the hypothesis is that dupilumab will decrease tissue eosinophils in patients with persistent asthma compared to placebo, as it was demonstrated in the R668-PH-17214 study that dupilumab potently blocked house dust mite-induced eosinophil infiltration into the lungs of *Il4rahu/hu Il4hu/hu* mice.
- Mast cells: tryptase positive, chymase positive.
- T lymphocytes: CD3 positive.

- T helper cells: CD4 positive.
- Goblet cells: MUC5 positive.
- B cells: CD23 positive.

The main endpoints will be the absolute change from baseline, the percent change from baseline as well as the ratio from baseline at Week 12/EOT for:

- The number of positive inflammatory cells per mm^2, derived by the biostatistics department, for each marker described above as:

$$\frac{\text{Number of positive inflammatory cells}}{\text{Total area of tissue assessed in mm}^2}$$

- For goblet cells (MUC5 positive) only, the following ratios will be also calculated by the biostatistics department:

- $\frac{\text{Total positive area assessed in mm}^2}{\text{Total area of tissue assessed in mm}^2}$
- $\frac{\text{Number of positive inflammatory cells}}{\text{Total positive area assessed in mm}^2}$

All IHC measurements will be assessed in triplicate; the mean of the 3 values will be used for all statistical analyses. Of note, the previous ratios will be calculated for each replicate first and then the 3 replicates will be averaged (the missing values will not be imputed and the average of the replicates will be calculated whatever the number of non missing values)

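### The on-treatment cut-off of last dose + 14 days falls on the nominal Week 12/EOT day with no visit tolerance, so some in-window biopsies from fully dosed patients drop out of every main endpoint

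*SAP*

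**What the plan says.** - **Cut-off.** Section 2.6, for pharmacodynamic data: "Only data measured before or on the last IMP date + 14 days (on-treatment period) will be taken into account in all analyses". Section 2.7.2 applies the same limit to efficacy. Neither states an exception.
- **Dosing.** Section 1.1: "every 2 weeks (q2w) for 12 weeks".
- **Visit timing.** Notes to Figure 1 in section 1.4: "Visit windows for visits after Day 1 are +/- 3 days". If the Week 12 bronchoscopy cannot be done, "the EOT visit may be postponed and up to 2 additional doses of IMP may be administered".
- **Main endpoints.** Section 2.6.1.1 defines them as absolute change, "the percent change from baseline as well as the ratio from baseline at Week 12/EOT". Bronchoscopy samples are taken only at baseline and Week 12/EOT (2.6.1), and missing values are not imputed (2.6.2.3).
- **Population.** Section 2.2.1 takes "all randomized and treated patients with an evaluable bronchoscopy performed at baseline and at Week 12/EOT", with no condition on timing after the last dose.
- **Sample size.** Section 1.3 needs 21 completers per group with adequate biopsies at both time points and makes no allowance for early dropout.

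**The concern.** One dosing interval after the last dose is a natural definition of the on-treatment period. Here it also decides whether a single scheduled assessment counts, and that assessment is planned for exactly the day on which the period ends. Half of the visit window therefore lies beyond the cut-off. A patient who took every dose and kept every visit window can still have the EOT biopsy set aside. No other post-baseline biopsy exists, so the patient is lost from every main endpoint, in a trial whose stated power assumes that all 21 biopsy pairs per group are usable.

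**Working it through.** **1. Where the cut-off falls.** The SAP text at hand does not state the day of the last regular dose, so it is inferred.
- Day 1 is the randomization day (2.11.3). Dosing every 2 weeks for 12 weeks gives Days 1, 15, 29, 43, 57 and 71.
- Doses given with a postponed EOT are described as additional (1.4), and Visit 8.1 at Week 12 is optional (2.8.2).
- Exposure is "last dose date - first dose date + 14 days" (2.4.1): 71 − 1 + 14 = 84 days, which is 12 weeks.
- The adverse event period ends 98 days after the last dose (2.8): 71 + 98 = Day 169, which is Week 24, the end-of-study visit (2.7.1.1).

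All of these fit a last regular dose on Day 71. The cut-off is 71 + 14 = Day 85, the Week 12 row of Table 7. The same coincidence arises when EOT is postponed to Week 14 or 16 with the extra doses given.

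**2. What the window allows.** The deciding quantity is the interval from the actual last dose to EOT.
- EOT booked from the last dose (one window): 14 ± 3, so 11 to 17 days. Intervals of 15, 16 and 17 days are excluded.
- Both visits varying around Day 1 (two windows): 14 + (EOT offset − dose offset), each offset from −3 to +3, so 8 to 20 days. Of the 49 combinations, 21 exceed 14 days.

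**3. Share lost (assumed timing).** Let p be the probability that a visit falls on the exact day, with q = (1 − p)/6 for each of the other six days.
- One window: P(over 14 days) = 3q.
- Two windows, visits independent: P(over 14 days) = [1 − (p² + 6q²)]/2.

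| p | One window | Two windows | Left of 21 (one / two) |
|---|---|---|---|
| 0.95 | 2.5% | 4.9% | 20 / 20 |
| 0.90 | 5.0% | 9.4% | 20 / 19 |
| 1/7 (uniform) | 42.9% | 42.9% | 12 / 12 |

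Example for p = 0.90, two windows: q = 0.0167; [1 − (0.81 + 0.0017)]/2 = 0.094.

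**4. Power.** Inputs from section 1.3: d = 25/32 = 0.781, one-sided 5%, two-sample t-test. Power is the probability that a non-central t with 2n − 2 degrees of freedom and non-centrality d√(n/2) exceeds the critical value. At n = 21 this gives 80.1%, which reproduces the stated 80%.

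| n per group | Power |
|---|---|
| 21 | 80% |
| 20 | 78% |
| 19 | 76% |
| 12 | 58% |

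**5. Eosinophil scale.** With the SAP's SD of 1.7 for the log ratio, the decrease detectable with 80% power is exp(1.7 × d). It is exp(1.7 × 0.781) = 3.77-fold at n = 21, matching the stated 3.8-fold. It becomes exp(1.7 × 0.801) = 3.90-fold at n = 20 and exp(1.7 × 1.048) = 5.94-fold at n = 12.

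**The case against.** **The convention is deliberate.** The + 14 days is one dosing interval. The SAP also uses it for exposure, for one of the concomitant medication summaries, for controller compliance and for the safety treatment epoch, and it keeps off-drug values out. This stands as a defence of the epoch. It does not explain why a scheduled assessment inside its own visit window should fail the rule. Assigning values to the theoretical visit (2.6) labels them but does not lift the cut-off.

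**The last dose is inferred.** The flow chart and protocol are not at hand and could show the dosing days and how EOT is booked. This stands as a limit on certainty, although every related passage of the SAP fits Week 10.

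**The loss may be small, and the trial is exploratory.** This stands. Tight booking costs one or two patients per group.

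Four stronger readings are tempting but not supported:
- *Section 2.6.2.3 contradicts 2.6 on FeNO.* It takes all post-baseline data until Week 12/EOT, whereas 2.6 sets + 14 days. But 2.7.2 combines both limits in one rule, so they are compatible. The FeNO paragraph merely lacks a cross-reference.
- *The population in 2.2.1 is inconsistent with the cut-off.* A population may contain patients without an analysable value. A timing condition there would also remove their baseline data from the summaries.
- *Every late EOT is lost.* A Day 88 EOT after a Day 74 dose is kept, while a Day 85 EOT after a Day 70 dose is excluded.
- *FeNO and spirometry lose power in the same way.* Their repeated-measures models keep the earlier visits, so the figures above do not carry over.

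**Conclusion.** The concern holds. Followed as written, section 2.6 excludes some in-window EOT biopsies from fully dosed patients, and each such patient leaves every main endpoint.

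The SAP gives no distribution of visit days, so the size of the loss is an assumption. With 90 to 95% of visits on the exact day, about 2.5 to 9% are lost, leaving 19 or 20 of 21 per group and power of about 76 to 78%. The 43% loss (12 per group, 58% power) requires visits spread uniformly over the window. It is an outer bound, not an expectation.

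The conclusion rests on a Week 10 last regular dose. The power figures use the SAP's own t-test assumptions and equal loss in both groups.

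**What to change.** Change the analysis window only, before database lock; the dosing and visit schedules stay as they are.

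- In 2.6 and 2.7.2, for the scheduled Week 12/EOT assessment only (including one postponed with the extra doses given), extend the cut-off by the visit tolerance: last dose + 17 days if EOT is booked from the last dose, or + 20 days if both windows are counted from Day 1. State which anchor applies.
- Report the + 14 day rule as a sensitivity analysis.
- In the FeNO paragraph of 2.6.2.3, add a cross-reference to the same cut-off as a clarification.
- Leave 2.2.1 unchanged. Values later than the extended limit, for example after a missed last dose or a postponed EOT without the extra doses, stay outside the on-treatment analysis.

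The cost is one sentence in each of 2.6 and 2.7.2, one cross-reference, a programming flag and the sensitivity run. The downside is that some retained values lie 1 to 3 days (+ 17) or 1 to 6 days (+ 20) past the dosing interval, and the pharmacodynamic and efficacy window will differ from the + 14 day treatment epoch used for safety.
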